9.2.2.12 Premature discontinuation (Dropout)

Section added by Amendment 2 (Modification 17).

If discontinuation occurs at the time of a scheduled visit, the appropriate measures/assessments for the timepoint (where possible) will be administered. The Social Media Questionnaire will also be administered (phone contact is acceptable).

If discontinuation occurs outside of a scheduled visit, attempts should be made to collect the following evaluations where possible (either by phone or in person):

- AE assessment, including but not limited to the following AEs of interest:
 - Infection, uterine or tubal perforation, device migration, device expulsion;
 - Allergic / hypersensitivity reactions, development of autoimmune-like symptoms.
- Device events (see Section 9.6.1.1 for details);
- Concomitant medications;
- Type of alternate contraception (if applicable);
- Pregnancy including pregnancy outcomes;
- Gynecological procedures such as endometrial ablation, hysterectomy, salpingectomy, oophorectomy, operative hysteroscopy, any other relevant gynecological events, and complications and outcomes including those associated with device removal (e.g., symptom resolution);
- Any new exposure to metals (e.g., piercings, orthodontics);
- Completion of Social Media Questionnaire.

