- **Rates of AEs in subjects undergoing Essure placement and laparoscopic tubal sterilization.** It is recognized that some AEs may be more likely to be reported in one group over the other during the course of the study, potentially due to outside influences (such as social media). To help control for this potential bias, the Supplemental PRO Questionnaires will actively solicit information on possible AEs related to depression, anxiety, pruritus, rash, pain in extremities, hair loss, nausea/vomiting, dysgeusia, fatigue, dental issues, and weight change in subjects in both groups. Active solicitation of AEs is likely to lead to higher rates of AEs than normally encountered; however, the influence should be the same on both groups.

Results of these tools will also be used to identify subjects with positive versus negative responses in order to create comparative groups for baseline and subsequent lab work.

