** Subjects completing ePRO questionnaires will receive email or text reminders to complete questionnaires 5 days prior to the scheduled completion date. The window for completion will be -5 days / +5 days for all questionnaires. If the questionnaire(s) are not completed by the scheduled completion date, another reminder will be sent and an alert will be sent to the site. Subjects completing paper questionnaires will not receive automated reminders and every effort will be made to ensure the subject completes the questionnaire within the window.

[‡] Subjects completing ePRO questionnaires will receive email or text reminders to complete questionnaires 1 week prior to the scheduled completion date. The window for completion will be -1 week / +2 weeks for all questionnaires. If the questionnaire(s) are not completed by the scheduled completion date, another reminder will be sent and an alert will be sent to the site. The subject and site will then receive weekly reminders and alerts at +1 week and +2 weeks. Subjects completing paper questionnaires will not receive automated reminders and every effort will be made to ensure the subject completes the questionnaire within the window.

^{§§} Subjects will complete Supplemental PRO Questionnaires at 12, 24, 36, 48, and 60 months. Subjects will complete a Social Media Questionnaire at 60 months (or Premature Discontinuation visit if applicable).

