9.2.3.3 Patient reported outcome measurement thresholds

Section modified by Amendment 2 (Modification 3).

This study will first employ a medically conservative and sensitive screening threshold to ensure capture of events in subjects that may not report concerns about their pain or bleeding to site investigators. The screening thresholds reflect the clinical judgment of Bayer investigators. Secondly, a more specific preliminary threshold for reporting AEs on the basis of PRO scores alone will be employed. These thresholds reflect scoring derived in instrument development and research experience with the scales.

For the Supplemental PRO Questionnaires related to mental health, a total response greater than or equal to 3 for either set of questions will prompt notification of the investigator; for the Supplemental PRO Questionnaires related to nausea/vomiting, any single response greater than or equal to 3 will prompt notification of the investigator. For the pruritus 5D itch scale, rash, pain in extremities, and fatigue scales, any response greater than or equal to 4 will prompt notification of the investigator. These thresholds were selected to ensure that subjects receive appropriate follow-up if they report medically important symptoms. There are no threshold triggers for hair loss, dysgeusia, dental care, or weight change. Upon notification about a threshold trigger on a Supplemental PRO Questionnaire, an investigator will assess the subject as he/she deems medically appropriate. If after assessment it is concluded that an AE has occurred, it must be captured on the appropriate AE eCRF. Additional information about these questionnaires is provided in Appendix 17.8.

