#### **4.6.3 Visit labels**

##### **General Rules**

For all the variables analyzed by visits, the values at scheduled visits will be used if available. If values at scheduled visits are missing but values are available at an associated unscheduled visit, the value from the closest unscheduled visit will be used to the scheduled visit.

If there are no values at scheduled or unscheduled visits, it will be considered as missing.

A value from the discontinuation visit (for discontinued subjects) will be assigned to the next scheduled visit (for the particular assessment per protocol) after the last visit the subject has completed.

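### Women who discontinue between scheduled visits get a general AE assessment and the Social Media Questionnaire, but not the pain screener, AMSS or Supplemental PRO that are meant to find unvolunteered events

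*Protocol*

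**What the plan says.** Protocol 9.2.2.12 treats two kinds of exit differently. For a woman who stops at a visit: "If discontinuation occurs at the time of a scheduled visit, the appropriate measures/assessments for the timepoint (where possible) will be administered", plus the Social Media Questionnaire. For a woman who stops between visits: "If discontinuation occurs outside of a scheduled visit, attempts should be made to collect the following evaluations where possible". That second list opens with "AE assessment, including but not limited to the following AEs of interest", continues with device events, medication, contraception, pregnancy, gynecological procedures and metal exposure, and ends with "Completion of Social Media Questionnaire". No other questionnaire is on it.

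Table 9-2 is consistent with this. As the table reads, the Premature Discontinuation column has an entry for the Social Media Questionnaire only, and the footnote says: "Subjects will complete a Social Media Questionnaire at 60 months (or Premature Discontinuation visit if applicable". The same footnote ties the Supplemental PRO to fixed months, with no discontinuation alternative.

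The purpose of the missing instruments is stated elsewhere. Protocol 9.2.3.3 sets the pain and bleeding screening thresholds "to ensure capture of events in subjects that may not report concerns about their pain or bleeding to site investigators". Under 5.2.1, a crossed threshold starts an AE investigation even if the woman has said nothing. Also in 5.2.1, the Supplemental PRO is the control for unequal AE reporting, on the ground that "the influence should be the same on both groups".

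SAP 4.6.3 says: "A value from the discontinuation visit (for discontinued subjects) will be assigned to the next scheduled visit". It gives no time limit.

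**The concern.** The main pain and bleeding endpoints are counted from AE reports, and the questionnaires are the plan's safeguard against silence. A woman who completes the study passes through all of them at Month 60 (9.2.2.11). A woman who leaves between visits is contacted and is given a questionnaire, but not one of those that open an AE work-up.

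SAP 4.3 keeps early leavers in the analysis populations, and subject incidence in SAP 6.4 and 6.4.1 ignores time at risk. An event she had but did not mention therefore counts as no event. If one arm loses more such women, that arm looks safer than it is.

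**Working it through.** The documents give no sample size, drop-out rate or effect size that bears on this point, so the check is a comparison of the schedule with the exit list.

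**1. Longest time without scheduled screening before a between-visit exit** (Table 9-2; look-back periods from Protocol Appendices 17.1, 17.4, 17.5 and 17.8):

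| Instrument | Longest gap | Look-back |
|---|---|---|
| Pain screener (PROMIS if positive) | 1 week in Weeks 1 to 4; about 1 month to Month 3; 3 months from Month 3 to 36; 12 months after Month 36 | 7 days |
| AMSS and intermenstrual questions | 3 months to Month 36; 12 months after | 3 months |
| Supplemental PRO | 12 months throughout | 12 months for most symptom items |

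For pain and bleeding, the 12-month gaps run from Month 36 to 48 and from 48 to 60: 12 + 12 = 24 of 60 months, or 40% of follow-up. For the Supplemental PRO they cover 5 × 12 = 60 of 60 months. If exits were uniform within an interval (an assumption), the mean unscreened time would be 3/2 = 1.5 months (range 0 to 3) or 12/2 = 6 months (range 0 to 12).

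**2. Which endpoints are exposed.** SAP 6.4 requires pain lasting more than 182 days. With 3-monthly screening, about 91 days apart, pain of that length at exit has spanned about 182/91 = 2 scheduled administrations. An episode that began inside the last 3 months cannot yet qualify. Chronic pain is therefore largely covered to Month 36. After that the gap is about 365 days, so an episode starting in roughly the first 365 − 182 = 183 days can become chronic before the next screen. AUB has no duration requirement and is exposed throughout. Hypersensitivity-type symptoms found through the Supplemental PRO are also exposed throughout.

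**3. Effect on crude incidence.** In arm *a*, let *d* be the share who leave between visits, and *q* the share of those with an event in the last interval that a questionnaire would have found but the AE assessment did not. Then observed incidence = true incidence − *d·q*, and observed risk difference = true risk difference − (*d·q* in the Essure arm − *d·q* in the laparoscopic arm). The error vanishes if the two products are equal. The documents give neither *d* nor *q* for either arm.

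**4. The SAP rule.** For between-visit leavers there is no AMSS, SF-36 or Supplemental PRO value to assign, and a PROMIS value exists only if pain was reported. Where a value does exist, one taken just after Month 36 would be labelled Month 48, up to 48 − 36 = 12 months ahead.

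**5. What the missing instruments would recover.** The AMSS would cover the whole open interval to Month 36, and 3 of up to 12 months (25%) after it. Most Supplemental symptom items would cover the whole interval. The pain screener sees only the last 7 days, but it would find ongoing pain, whose onset the AE work-up can then date.

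**The case against.** Much of the opposing case stands.

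- The exit contact does ask about AEs. The wording is that of the routine contacts from Month 3 to Month 60, so the fact that pain and bleeding are not named is not peculiar to drop-out. Allergic and autoimmune-like symptoms are named.
- PROMIS 3a and 8a must be given off-schedule when pain is spontaneously reported (5.2.1, 9.2.3.1, Table 9-2).
- Not repeating the AMSS off-schedule is a stated decision (5.2.1, 9.2.3.1), so editing 9.2.2.12 alone would create a contradiction. The stated reason is that the next 3-monthly administration captures the data. That fails for a woman who has no next administration, and it weakens for everyone after Month 36.
- Kaplan-Meier estimates censor an early leaver and exposure-adjusted incidence stops her clock. Only crude incidence keeps her in the denominator as a non-event.
- Women lost to follow-up have no exit contact and would gain nothing from a longer list.
- The study is exploratory and longitudinal PRO analysis is descriptive.

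One objection does not stand: that screening only leavers would add ascertainment to the arm that loses more women. For women who stay, each interval is closed by a scheduled screen. A screen at exit closes the leaver's interval in the same way.

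**Conclusion.** The gap is real but narrower than it may first appear. For between-visit exits, the last interval lacks questionnaire-based solicitation for up to 3 or 12 months, as tabulated. Unvolunteered AUB and hypersensitivity-type events can be missed, and chronic pain mainly after Month 36.

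The documents do not support three stronger readings that a reader might infer:

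- That the interval is wholly unsolicited, or that no pain instrument is ever used. AE assessment heads the list and PROMIS follows a pain report.
- That the SAP rule has no PRO data at all. Women who stop at a scheduled visit supply it, an off-schedule PROMIS can be used, and the rule also covers non-PRO variables.
- That the arm comparison is biased in a known direction. The media attention cited in Protocol 10.1 concerns the choice of procedure. Neither document says that drop-out will differ by arm or gives a rate.

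Bias requires between-visit drop-out with unvolunteered events to differ between arms, and its size cannot be computed from the documents. This is a worthwhile low-cost improvement, not a flaw that undermines the study.

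**What to change.** - **Protocol 9.2.2.12 and the Premature Discontinuation column of Table 9-2:** add, where possible, the pain screening question (with PROMIS 3a and 8a if positive), the AMSS with the two intermenstrual questions, and the Supplemental PRO. Keep the existing thresholds and AE assessment.
- **Protocol 5.2.1 and 9.2.3.1:** make discontinuation an exception to the rule that the AMSS is not repeated off-schedule.
- **SAP 4.6.3:** assign a discontinuation value to the next scheduled visit only if it falls within that assessment's window. Otherwise report it as a discontinuation value and use it for event detection only. This change can be made even if the protocol is not amended.

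The cost is amendment wording and one more set of instruments already in use, at a contact that already gives a questionnaire. The departing woman spends a few more minutes and may decline. The change does not reach women lost to follow-up, and recall limits what it recovers: 7 days for the pain screener and 3 months for the AMSS.

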9.2.3 Patient reported outcome measurements

9.2.3.1 Patient reported outcome data capture system

Section modified by Amendment 1 (Section 16.1) and Amendment 2 (Modification 3).

A web-based, electronic data capture system will be available to record PRO measure data in this study. The proposed system will integrate programming that tracks scheduled PRO response compliance with reminder notifications (email or text) to subjects for each scheduled administration of the questionnaires.

The system will provide for a window for completion of PRO instruments at the cross-section, sending the first message to respond to online PRO in anticipation of the ideal scheduled date, according to the windows described in Table 9-2. If the subject fails to respond, a reminder will be sent on the scheduled date encouraging the subject to complete the online questionnaires. If the respondent still fails to respond, a flagged, urgent reminder will be sent both to the subject and to the site investigator, triggering a telephone reminder to the subject to complement the emailed message. Finally, toward the end of the response window, a follow-up email or text will be provided automatically to both the subject and the site prior to closing availability of the questionnaire being implemented indicating a “last chance” for PRO completion if needed.

The system will also be programmed to generate notifications to site investigators triggered by specified subject item response and total score thresholds. For the alerts such as those related to pain and bleeding, site investigators will be required to assess potential AEs for subjects in whom potential AEs have not already been recently assessed.

For subjects who wish to complete the PRO measurements on paper, questionnaires will be mailed to the subject by the site in accordance with the completion windows noted in

Table 9–2. No automated reminders will be sent. Subjects will complete the paper questionnaires and return the questionnaires to Covance via courier. Once received, if the date on the questionnaire is within the appropriate window, the questionnaire data will be entered into the electronic data capture system by an independent data entry group.

If a potential pain event is spontaneously reported outside of a scheduled visit or scheduled PRO tool administration, the pain PRO tools (PROMIS V1.0 – Pain Intensity 3a and PROMIS Scale V1.0 – Pain Interference 8a Participant Format) will be administered off-schedule in order to characterize pain intensity and interference. If a potential bleeding AE is reported at a scheduled visit or if the subject spontaneously reports such an event to the site at some other time, the event will be evaluated per standard AE assessment. In the event of a report outside of a scheduled visit or scheduled PRO administration, the Aberdeen Menorrhagia Severity Scale (AMSS) and two intermenstrual bleeding questions will not be re-administered as the recall period for these PRO tools is 3 months and these data are captured during the scheduled PRO tool administration which occurs every 3 months.

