5.2 Endpoints and variables

5.2.1 Main endpoints

Section modified by Amendment 1 (Section [16.1](#)) and Amendment 2 ([Modification 3](#), [Modification 4](#), [Modification 5](#), [Modification 7](#)).

- **Pain:** The proportion of subjects reporting AEs of chronic lower abdominal and / or pelvic pain after insertion of Essure System compared to the proportion of subjects reporting AEs of chronic lower abdominal and / or pelvic pain after laparoscopic tubal sterilization. Total incidence of pain events will be based on AE reporting. If a potential pain event is spontaneously reported outside of a scheduled visit or scheduled patient-reported outcome (PRO) tool administration, the pain PRO tools (Patient-Reported Outcomes Measurement Information System [PROMIS] Scale V1.0 – Pain Intensity 3a and PROMIS Scale V1.0 – Pain Interference 8a Participant Format; see Section [9.2.3](#)) will be administered off-schedule in order to characterize pain intensity and interference. If during the course of a scheduled PRO administration (see [Table 9–2](#) and Section [9.2.3](#)) the subject reaches a preset threshold for pain on a PRO tool, even if she has not spontaneously reported a pain event to the investigator, the investigator will be alerted and instructed to investigate this finding in order to determine whether or not an AE has occurred. Standard criteria for AE assessment (e.g., new or worsening symptom) will be used and all investigators will be trained on standard AE assessment.

The preset thresholds that will trigger investigation of pain as an AE are as follows: on the PROMIS Pain Intensity Scale, a score of 3 (moderate intensity) for the ‘pain at its worst’ question will trigger investigation regardless of the other scores or results of the PROMIS Pain Interference Scale. For PROMIS Pain Interference Scale, a t-score of ≥ 60 (which corresponds to a raw score of ≥ 22) or any single item raw score of ≥ 4 will trigger investigation regardless of the results of the PROMIS Pain Intensity Scale. Section [9.2.3](#) includes justification for these thresholds. Not all reports of pain that are reported on the PRO tool will be considered AEs. This is particularly notable in the case of a subject who has pre-existing pain that continues to be unchanged post-sterilization procedure.

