28 JUN 2022

Version 5.0

Page: 34 of 149

Table 9–2 Schedule of PRO evaluations

Questionnaire	Baseline	Week 1 [§]	Week 2 [§]	Week 3 [§]	Week 4 [§]	Month 2**	Month 3 [‡]	Month 6 [‡]	Month 9 [‡]	Month 12 [‡]	Month 15 [‡]	Month 18 [‡]	Month 21 [‡]	Month 24 [‡]	Month 27 [‡]	Month 30 [‡]	Month 33 [‡]	Month 36 [‡]	Month 48	Month 60	Premature Discontinuation (Dropout)
PROMIS Scale v1.0 – Pain Intensity 3a ^{*†}	•	•	•	•	•	•	•	•	•	•	•	•	•	•	•	•	•	•	•	•	
PROMIS Scale v1.0 – Pain Interference 8a Participant Format ^{*†}	•	•	•	•	•	•	•	•	•	•	•	•	•	•	•	•	•	•	•	•	
Aberdeen Menorrhagia Severity Scale; and two intermenstrual bleeding questions	•						•	•	•	•	•	•	•	•	•	•	•	•	•	•	
SF-36	•							•		•				•				•		•	
Fibromyalgia Survey Questionnaire	•																				
Supplemental PRO Questionnaires										•				•				•	•	• ^{§§}	
Social Media Questionnaire																			• ^{§§}	•	

PRO=patient reported outcome, PROMIS=patient reported outcome measurement information system, SF-36=Short Form-36.

*All subjects are asked screening question “Did you experience pain in your pelvic area or in your lower abdomen during the past week?” Subjects that answer “Yes” complete both the PROMIS Scale v1.0 – Pain Intensity 3a and PROMIS Scale v1.0 – Pain Interference 8a Participant Format. Subjects that answer “No” do not have to complete the questionnaires.

[†] In the event a subject spontaneously reports an adverse event of pain, the subject will be given both the PROMIS Scale v1.0 – Pain Intensity 3a and PROMIS Scale v1.0 – Pain Interference 8a Participant Format questionnaires to complete at the time of reporting.

[§] Subjects completing ePRO questionnaires will receive email or text reminders to complete questionnaires 2 days prior to the scheduled completion date. The window for completion will be -2 days / +2 days for all questionnaires. If the questionnaire(s) are not completed by the scheduled completion date, another reminder will be sent and an alert will be sent to the site. Subjects completing paper questionnaires will not receive automated reminders and every effort will be made to ensure the subject completes the questionnaire within the window.

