For subjects with a second placement procedure, any PROMIS 3a and 8a PRO data collected after baseline and up to and including Month 3 will be repeated based on the timing of the second placement procedure (See Section 9.2.2.3 for additional details). For summaries by time point (e.g., Week 1), only the final evaluation will be included in the analyses. For time-to-event endpoints or proportion of subjects meeting a given criterion, all collected data will be used.

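### As written, a paper questionnaire dated outside its completion window has no route to a safety alert or to the PRO data

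*Protocol*

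**What the plan says.** Protocol Section 9.2.3.1 offers paper as an alternative to the electronic questionnaires. On the route of the forms it says: "Subjects will complete the paper questionnaires and return the questionnaires to Covance via courier". On entry it says: "if the date on the questionnaire is within the appropriate window, the questionnaire data will be entered into the electronic data capture system". Alerts are described in the same section as a function of the electronic system: "The system will also be programmed to generate notifications to site investigators triggered by specified subject item response and total score thresholds".

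The windows are in the footnotes to Table 9-2 (Section 9.1). For Weeks 1 to 4: "The window for completion will be -2 days / +2 days for all questionnaires". For Month 2 it is 5 days either side, and for Months 3 to 36 it is 1 week before to 2 weeks after. The Month 48 and Month 60 columns carry no window. The footnotes add: "Subjects completing paper questionnaires will not receive automated reminders and every effort will be made to ensure the subject completes the questionnaire within the window".

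The purpose of the alerts is stated twice. Section 9.2.3.3: "This study will first employ a medically conservative and sensitive screening threshold to ensure capture of events in subjects that may not report concerns". Section 5.2.1, on pain: "even if she has not spontaneously reported a pain event to the investigator, the investigator will be alerted".

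**The concern.** A completion window is a sensible rule for deciding which visit a score belongs to. Here it also decides whether a completed symptom report is read at all. The PROs are the study's means of finding events that women do not volunteer, and alerts feed the investigator's AE assessment for pain and abnormal bleeding. PRO-identified pain and bleeding events are also flagged and reported as such (Section 9.2.3.4.1), and SAP Table 2 reports the percentages of subjects above the score cut-offs.

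A form left unentered could therefore cost medical follow-up, an AE that alert-driven assessment would have found, and a PRO outcome. Bleeding has little slack: Section 9.2.3.1 does not re-administer the AMSS after an off-schedule bleeding report, because it relies on the scheduled form to capture those data. The next AMSS has a 3-month recall and largely describes a different quarter.

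**Working it through.** The plan states no figure to reproduce. The check follows the route of a form and then counts days and forms.

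**1. Route of an out-of-window paper form.** Completed at home, couriered to the contractor, date checked, condition not met. No further step is described: no entry with a flag, no manual review, no copy to the site. Since the alert comes from the electronic system, a form that is not entered has no described way to raise one. SAP Section 4.6.3 lets the closest unscheduled value stand in for a missing scheduled one, but only among values already in the database.

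**2. Window widths** (days before + days after + 1, from Table 9-2).
- Weeks 1 to 4: 2 + 2 + 1 = 5 days
- Month 2: 5 + 5 + 1 = 11 days
- Months 3 to 36: 7 + 14 + 1 = 22 days
- Months 48 and 60: none stated

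**3. Number of forms after baseline** (Table 9-2).
- Pain screen: 4 (Weeks 1 to 4) + 1 (Month 2) + 1 (Month 3) + 11 (Months 6 to 36) + 2 (Months 48, 60) = 19. With a stated window: 19 − 2 = 17.
- AMSS: 1 + 11 + 2 = 14. With a stated window: 14 − 2 = 12.

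**4. Forms without a paired AE contact.** Sections 9.2.2.4 to 9.2.2.11 schedule AE assessment at Week 1 and Months 3, 12, 24, 36, 48 and 60.
- Pain: 19 − 7 = 12 unpaired (Weeks 2, 3, 4; Months 2, 6, 9, 15, 18, 21, 27, 30, 33).
- AMSS: 14 − 6 = 8 unpaired (Months 6, 9, 15, 18, 21, 27, 30, 33).
- Supplemental questionnaires (Months 12, 24, 36, 48, 60): 5 − 5 = 0 unpaired.

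All the unpaired pain and AMSS forms fall at time points that do have a window.

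**5. PRO window against visit window.** The 12-, 24- and 36-month visits allow 28 + 28 + 1 = 57 days. The PRO window covers 22 of them, so 57 − 22 = 35 days (35/57 = 61%) are acceptable for the visit but not for the form. At the 3-month contact the laparoscopic group has 14 + 14 + 1 = 29 permitted days, of which 7 (days −14 to −8) lie outside the PRO window. The Essure group has 0 + 14 + 1 = 15, of which none do. These are shares of calendar days, not of forms.

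**6. Illustration only.** The documents give no share of out-of-window paper forms. If it were 10%, 20% or 30% (assumption), a paper user would have 17 × share = 1.7, 3.4 or 5.1 pain screens and 12 × share = 1.2, 2.4 or 3.6 AMSS forms refused. An episode visible at one screen only would go unseen by the PRO with probability 10%, 20% or 30%. Pain of 6 months or longer spans about two quarterly screens. With independent lateness, both are refused with probability share² = 1%, 4% or 9%; if the same women are always late, the figure rises towards the single-screen value.

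**The case against.** The strongest points on the other side are these.

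- **Other routes to the event exist.** The main pain and bleeding endpoints rest on AE reporting, not on PRO scores. AEs are assessed at seven scheduled contacts and on spontaneous report, and a spontaneous pain report leads to off-schedule PROMIS. This stands. A reader might infer that the reports are lost; the documents support only that they may be missed or delayed. The backup is weakest for the woman who does not volunteer the event, which is the case the alert exists for.
- **Electronic questionnaires also close at the end of the window.** This stands as a limit on analysis: taking late paper forms into between-group proportions would give paper users a longer reporting period. It does not justify leaving a completed form unread. Electronic closure prevents a late report, whereas the paper rule ignores one already returned.
- **The windows are wider than the Week 1 to 4 figure suggests.** A reader might infer that any form a few days late is dropped. A form dated 3 days late fails only for the Week 1 to 4 pain questionnaires. AMSS and supplemental forms through Month 36 must be more than 7 days early or 14 days late. The test is the date on the form, so courier delay alone excludes nothing.
- **Sites must make every effort to obtain forms in the window, and they mail them to fit it.** This may keep the numbers small. It supplies no rule for when the effort fails.
- **Section 10.3 says that "For time-to-event endpoints or proportion of subjects meeting a given criterion, all collected data will be used".** That sentence concerns repeated PROMIS data after a second placement. It is a useful precedent, but it does not reach a form that was never entered.

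**Conclusion.** The concern holds as a defect in a stated rule. As Section 9.2.3.1 is written, a returned paper form dated outside its window reaches neither the alert system nor the PRO data, and nothing else in the protocol or SAP picks it up. That such forms are not entered is the plain implication of the conditional sentence; it is not said outright.

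The exposure is confined to paper users with events they do not otherwise report, and mainly to the 12 pain screens and 8 AMSS forms that fall between AE contacts. The supplemental symptom forms all coincide with an AE contact and are better protected. The conflict between PRO and visit windows makes a failed entry test possible even at an on-time visit.

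The number of forms affected cannot be computed. The 10% to 30% range above is an assumption, and its single-screen miss rates must not be read as the effect on chronic pain. A reader might also infer a bias between the groups. Paper use could differ by group, and paper users get no automated reminders, but the documents do not show that use differs or that paper forms are later. With unknown frequency, other capture routes and exploratory analyses, this is a should-fix rather than a must-fix.

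**What to change.** Change Section 9.2.3.1 so that every returned paper form is entered on receipt, with an out-of-window flag where it applies, and the existing alert thresholds are run on it. Then:

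- In SAP Section 4.6.3, leave flagged forms out of by-visit summaries.
- Report the proportions with PRO-identified events with and without flagged forms, because the electronic questionnaires close at the end of the window.
- State in Table 9-2 which window applies at Months 48 and 60.
- If returned forms that were not entered have been kept, enter them and send the resulting alerts to the sites. The documents do not say whether any exist.

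The cost is a short protocol change, a revised data-entry instruction, one flag variable and some extra data entry. The forms concerned have already been completed, so subjects carry no added burden.
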